### 2.5.2 Primary Analyses:

Recovery of Responsiveness: Given that the induction of generalized seizures by electrical stimulation may compound the recovery from general anesthesia, we expect that interval from loss to return of responsiveness following ketamine + ECT will be longer compared to the period for ketamine + sham ECT. We will determine the median and 95% confidence intervals for this measure in relation to the treatment intervention.

Recovery of Cognition: Given that postictal suppression may be prolonged with ketamine than with etomidate(Hoyer, Kranaster et al. 2014), we hypothesize that the time needed for the return of cognition to baseline on individual sessions will be greatest for ketamine + ECT, followed by etomidate + ECT, and ketamine + sham ECT. Separate mixed-effects models will be generated based on reaction time and accuracy. We will determine the time of convergence for 95% confidence intervals for the marginal responses related to

the three treatment groups. To determine the timing for the recovery to baseline, we will determine the time when the same 95% confidence intervals include 0.

Postictal Delirium and Cognitive Recovery: We expect the incidence of delirium (3D-CAM) to be associated with delayed restoration of baseline function in all cognitive domains. The magnitude and significance of this relationship will be determined from the mixed effects models for each cognitive test.

Comparison of Cognitive Recovery After ECT and Isoflurane General Anesthesia: We hypothesize that the time for recovery to baseline will be quicker for treatments involving ECT compared to that for the recovery from isoflurane general anesthesia. Convergence for 95% confidence intervals will be compared between treatment groups.

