#### 2.2 Hypotheses and Aims

We hypothesize that the reconstitution of cognitive function will markedly vary in rate and order, depending on the presence of seizures induced by electrical brain stimulation. Our specific aims include: (1) assess whether the time to return of responsiveness will be prolonged with ketamine + ECT compared with ketamine + sham ECT; (2) ascertain whether the time of restoration to baseline function in each cognitive domain will take longer after ketamine + ECT than after ketamine + sham ECT; (3) determine if postictal delirium is associated with delayed restoration of baseline function in all cognitive domains; and (4) determine whether the sequence of reconstitution of cognitive domains is similar to that occurring after an isoflurane general anesthetic; we also anticipate these cognitive disturbances

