#### 2.5.1 Statistical Analysis

We will employ mixed-effects models to quantify trajectories of cognitive recovery over time while addressing inter-subject variance and missing data. Linear models with appropriate transformations will be used preferentially over non-linear models. Time and treatment intervention group will be included as fixed effects while random effects will account for repeated measures provided by each participant. Day of treatment relative to the dose-charge titration session will allow consideration of cumulative effects of treatment order that may remain biased despite randomization. To address differences in ECT-stimulation responsiveness, regression approaches will account for dose charge, central seizure duration, and age. Models will assess for the effects of treatment on the timing for the return of responsiveness to verbal command and the presence of delirium. Separate mixed-effects models will be generated to assess task performance in a group of young healthy volunteers during the recovery from isoflurane general anesthesia (Maier, McKinstry-Wu et al. 2017).

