### 2.5.3 Secondary Analyses

Recovery of Cognition: Principal measures of performance are based on preliminary data(Basner, Savitt et al. 2015) of the Cognition test battery. Additional measures include: PVT response speed, DSST throughput, PVT lapses, VOLT duration and accuracy, AM duration and accuracy, and DSST errors. Cognition performance measures associated with lower effect sizes will also be assessed. These include AM accuracy, VOLT accuracy, F2B reaction time, MPT accuracy, MPT duration, and F2B accuracy. Overall, we expect F2B, VOLT, and AMT to recover the slowest due to taxing of short-term memory after ketamine + ECT compared to ketamine + sham ECT.

Recovery in the Spontaneous EEG: We will evaluate mixed-effects models to test the hypotheses that the predominance of frontal delta or theta power during passive eyes opening or occipital alpha power during eyes closed predict cognitive performance (Cognition scores) or delirium (3D-CAM scores). We will also compare these EEG spectral measures across treatment sessions to evaluate the impact of anesthetic and ECT. Relationship of ECT Seizure Duration to Return of Responsiveness to Verbal Command: We expect that the length of ECT-induced seizures will correlate with the intervals from the loss of responsiveness to the return of responsiveness.

Mood and Depression Severity: We expect improvement in these clinical outcomes to be greatest with ketamine + ECT, followed by etomidate + ECT, and then ketamine + sham ECT.

16

Treatment Satisfaction: We expect satisfaction to be greatest for ketamine + ECT, followed by ketamine + sham ECT, and then by etomidate + ECT.

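### Recovery to baseline is declared when a 95% confidence interval includes 0, so an undetected deficit counts as recovery; the rule for comparing groups, interval convergence, is not defined

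*Combined protocol and SAP*

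**What the plan says.** Section 2.5.2 (Recovery of Cognition) gives two rules for reading results from the mixed models of Section 2.5.1.

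- **Comparing the three treatments:** "We will determine the time of convergence for 95% confidence intervals for the marginal responses related to" the three treatment groups.
- **Dating the return to baseline:** "we will determine the time when the same 95% confidence intervals include 0".

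For the isoflurane volunteers, who are modelled separately, Section 2.5.2 says: "Convergence for 95% confidence intervals will be compared between treatment groups".

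These rules serve two aims in Section 2.2. Aim 2 asks whether "the time of restoration to baseline function in each cognitive domain will take longer after ketamine + ECT" than after ketamine with sham ECT. Aim 4 is to "determine whether the sequence of reconstitution of cognitive domains is similar to that occurring after an isoflurane general anesthetic".

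On the model, Section 2.5.1 says: "Time and treatment intervention group will be included as fixed effects while random effects will account for repeated measures provided by each participant". It names no treatment-by-time term, and Section 2.5.2 names no contrast for cognitive recovery. No section gives a margin, a smallest deficit that matters, or a definition of convergence. That 0 means no change from baseline has to be inferred.

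**The concern.** Failing to reject a zero deficit is not evidence that the deficit is zero. Under the stated rule, a mean deficit passes as recovered once it is smaller than about 1.96 standard errors. For the same raw deficit, a noisier test, a smaller sample or a less precisely estimated cohort therefore tends to be declared recovered sooner. Recovery timing is a primary outcome, and a date that depends partly on precision is hard to interpret even descriptively.

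The second rule cannot be carried out as written. Convergence could mean that two intervals overlap, that one covers the other's estimate, or that the interval for the difference covers 0. These behave very differently. The first two ignore that each patient receives all three treatments, which Sections 2.3.5 and 2.7.1 present as the strength of the design.

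**Working it through.** The plan states no operating figure for either rule, so there is none to reproduce. The SDs in Section 2.6 are in minutes and do not apply to a test score.

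**Inputs from the document.** 15 to 20 patients (Synopsis, Section 2.6); each treatment given twice (Section 2.7.1); tests at 0, 30, 60 and 90 minutes (Appendix 1).

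**Assumed.** SD of change from baseline = 1; correlation r between a patient's two sessions on one treatment from 0 to 0.5; each test time analysed alone.

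**Step 1: deficit accepted as recovered.** SE = √((1+r)/2)/√n. The accepted deficit is 1.96 × SE.

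**Step 2: chance that a true deficit d = 0.5 SD is called recovered.** With normal quantiles, P = Φ(1.96 − d/SE) − Φ(−1.96 − d/SE). The last column uses the noncentral t on n − 1 degrees of freedom.

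| n | r | SE | 1.96 × SE | d/SE | P (normal) | P (t) |
|---|---|---|---|---|---|---|
| 15 | 0 | 0.183 | 0.36 | 2.74 | 22% | 28% |
| 15 | 0.5 | 0.224 | 0.44 | 2.24 | 39% | 45% |
| 20 | 0 | 0.158 | 0.31 | 3.16 | 11% | 15% |
| 20 | 0.5 | 0.194 | 0.38 | 2.58 | 27% | 31% |

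**Step 3: effect of precision alone.** Keep the deficit at 0.5 and multiply the n = 15 standard errors by a hypothetical 1.5. Then d/SE is 1.83 to 1.49 and P rises from 22–39% to 55–68% (normal quantiles). The true deficit has not changed.

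**Step 4: convergence read as overlap.** Two intervals with equal SEs fail to overlap when the estimates differ by more than 2 × 1.96 × SE = 3.92 SE. The SE of the difference is SE × √(2(1−ρ)), where ρ is the correlation between the two arms' estimates. The implied critical value is k = 3.92/√(2(1−ρ)), and alpha = 2(1 − Φ(k)). Where the paired contrast has 80% power (standardised difference 1.96 + 0.84 = 2.80), the overlap rule has power 1 − Φ(k − 2.80).

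| ρ | k | alpha | power |
|---|---|---|---|
| 0 | 2.77 | 0.6% | 51% |
| 0.3 | 3.31 | 0.09% | 30% |
| 0.5 | 3.92 | 0.009% | 13% |

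If convergence instead means that one interval covers the other arm's estimate, k = 1.96/√(2(1−ρ)). Alpha is then 17% at ρ = 0 and 5% at ρ = 0.5. At ρ = 0 the undefined word leaves alpha at 0.6% or 17%.

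**The case against.** **The study is exploratory and the models are already planned.** Section 2.5 calls the study exploratory, and the planned models yield marginal responses with intervals, so most of what is needed is close to existing output. This stands, and it lowers both the weight and the cost. It does not supply a recovery rule or a meaning for convergence, and both rules sit under Primary Analyses.

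**The figures are assumed, and a fitted curve would be more precise.** This also stands. In the most favourable case, a correct quadratic time curve is fitted to the four tests and all variation is independent test-to-test noise. The 60-minute fitted value then has leverage 1 − 9/20 = 0.55 and SE = √(0.55/(2n)). The accepted deficit falls to 0.27 SD at n = 15 and 0.23 SD at n = 20, and a 0.5 SD deficit passes in 4% and 1% of trials. Stable differences between patients or sessions move these figures back towards the single-time values. The mechanism does not depend on any particular SD.

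**A margin is hard to meet with this sample.** If an upper confidence bound had to fall below 0.5 SD, with true deficit 0, one value per patient, one-sided 0.025 and 80% power, n = ((1.96 + 0.84)/0.5)² = 31.4, or 32 patients. That exceeds the target, so the proposed margin applies to the point estimate.

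**Stronger readings that a reader might infer, and that the documents do not support:**

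- *The rule biases the comparison of the randomized arms.* With a common-variance model and balanced data, the arms have equal SEs and there is no differential bias. It would need arm-specific variances or unequal missing data.
- *The isoflurane comparison is biased in a known direction.* Neither the size nor the SD of that cohort is given, so the direction is unknown.
- *The rule works against the plan's own expected order of domains.* Section 2.5.3 says "we expect F2B, VOLT, and AMT to recover the slowest due to taxing of short-term memory" and also says "Cognition performance measures associated with lower effect sizes will also be assessed". But the first sentence goes on to compare ketamine plus ECT with ketamine plus sham ECT, so it is at least partly a between-arm expectation. The effect-size ranking appears to rest on preliminary data from the cited battery source, and AM and VOLT accuracy appear in both lists of measures. Nor does a test with a smaller standardised deficit that is declared recovered earlier show an artefact, because it may really be closer to baseline.

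**Conclusion.** The recovery rule is wrong as written. It counts a deficit of up to about 1.96 SE as recovery and lets precision help to set the date. With 15 to 20 patients and the assumptions above, that is roughly 0.3 to 0.4 SD, and a 0.5 SD deficit would often be missed. The size depends on those assumptions; the defect does not. For equal raw deficits, a test or cohort with a larger SE tends to be declared recovered earlier. That is a tendency, not a certainty in any one dataset.

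The comparison rule is undefined. The overlap figures hold only if convergence means overlap with equal SEs; on that reading, real differences between treatments would often be called converged. Confidence is high on these two points and does not extend to the stronger readings set aside above. Because the study is exploratory, this is a should-fix.

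**What to change.** Change Section 2.5 as follows.

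1. Replace convergence of intervals with model-based within-patient contrasts between the three treatments (ketamine + ECT minus ketamine + sham, ketamine + ECT minus etomidate + ECT, etomidate + ECT minus ketamine + sham) at 0, 30, 60 and 90 minutes, each with a 95% confidence interval. Fit them from a model that includes treatment-by-time; without that term the fitted arms are parallel.
2. Do not call an interval that includes 0 recovery. Report the fitted deficit from the same session's baseline, with its 95% confidence interval, at each time.
3. If a recovery time is quoted, define it as the time when the fitted mean deficit (the point estimate, not a confidence bound) falls within one prespecified margin per test, identical across arms and the isoflurane cohort. Report it, and differences in it, with 95% confidence intervals from a bootstrap that resamples participants. Report curves or bootstrap draws that do not cross by 90 minutes as >90 min.

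**Cost.** Rewording and some analysis code; no new data. Each margin is a judgement to be made in advance, since the documents give no basis for one. Reported recovery times may be later or less certain.

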### **Experimental Treatment Visits (Visit 2-7)**

Baseline assessments will be performed at each session immediately prior to ECT and will include a cognitive battery (COGNITION), electroencephalography, depression testing (PROMIS-CAT) and mood assessment (Self-Assessment Manikin), suicidal ideation (Scale of Suicidal Ideation)(Beck, Kovacs et al. 1979), and the 3D Confusion Assessment Method (3D-CAM). Details regarding these assessments are provided as an appendix at the end of the protocol.

During four of these six sessions, the patients will receive care that is currently within standard practice for ECT: general anesthesia (standard of care or ketamine), muscle paralysis (succinylcholine), and electrical stimulation. For the remaining two sessions, patients will undergo a ketamine general anesthetic without muscle paralysis or ECT stimulation.

High-density EEG, bilateral fronto-mastoid clinical EEG, and full American Society of Anesthesiologists (ASA) monitoring will commence prior to the induction of general anesthesia. Prior to induction, audible squeeze toys will be placed in each hand of the patient, who will be instructed to follow serial commands to either "Squeeze your left hand twice" or "Squeeze your right hand twice." Every 30 seconds, one of these commands will be played at random, to monitor loss and return of consciousness. Patients will be pre-oxygenated by mask and

11

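### The cognition analysis appears to model change from each session's baseline without adjusting for that baseline, so between-arm contrasts may carry avoidable noise

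*Combined protocol and SAP*

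**What the plan says.** Section 2.3.8 (Experimental Treatment Visits) has the cognitive battery done before every experimental session: "Baseline assessments will be performed at each session immediately prior to ECT". Table 1 in the appendix shows the same.

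Section 2.5.2 takes as its target "the time needed for the return of cognition to baseline on individual sessions". It has two readouts. The arms are compared by interval convergence: "We will determine the time of convergence for 95% confidence intervals for the marginal responses". Recovery within an arm is timed by a comparison with zero: "we will determine the time when the same 95% confidence intervals include 0".

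Section 2.5.1 gives the model: "Time and treatment intervention group will be included as fixed effects while random effects will account for repeated measures provided by each participant". It adds an order term ("Day of treatment relative to the dose-charge titration session will allow consideration of cumulative effects of treatment order") and three covariates ("regression approaches will account for dose charge, central seizure duration, and age"). The pre-session cognitive score does not appear, and the scale of the response is not stated.

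**The concern.** A raw reaction time or accuracy would not be compared with 0, so the rule makes sense only if the response is a difference from baseline. The phrase about individual sessions points to that session's own baseline.

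Each patient receives every treatment twice, so the patient effect already removes stable differences between patients. Subtracting one session's baseline does not repeat that job. It brings the baseline's session-to-session error into every post-treatment value from that session. Entering the baseline as a covariate lets the data decide how much of it to subtract.

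The target is 15-20 patients, so precision is scarce. Both readouts also depend on interval width: a wider interval includes 0 sooner, and wider arm intervals overlap sooner. Unneeded noise would therefore cost power and also make recovery and convergence look earlier.

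**Working it through.** **The plan's own figure.** The plan gives no pre/post correlation and no precision for a cognition contrast. Its only related figure is the conservative sample size of 24 in section 2.6 (difference 20 min, SD 20 min, two-sided alpha 0.05, 80% power). With the 6 pairs among 4 means, n = 2[σ(z for 1 − 0.05/12 + z for 0.80)/Δ]² = 2(2.638 + 0.842)² = 24.2, which reproduces it. That calculation is in minutes of recovery time, whereas the models are to be fitted to test scores. A variance ratio for scores cannot be carried over to it.

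**Contrast variance at one testing time.** Inputs, both assumed: r = 0.2, 0.5, 0.7 and k = 1, 1.5, 2. Let s be the within-patient SD of the pre-session score and ks that of the post-session score.

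- Change score: s²(1 + k² − 2rk)
- Baseline-adjusted: k²s²(1 − r²)
- Ratio, adjusted to change: k²(1 − r²)/(1 + k² − 2rk)

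| k | r = 0.2 | r = 0.5 | r = 0.7 |
|---|---|---|---|
| 1 | 0.96/1.60 = 0.60 | 0.75/1.00 = 0.75 | 0.51/0.60 = 0.85 |
| 1.5 | 2.16/2.65 = 0.82 | 1.6875/1.75 = 0.96 | 1.1475/1.15 = 1.00 |
| 2 | 3.84/4.20 = 0.91 | 3.00/3.00 = 1.00 | 2.04/2.20 = 0.93 |

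At k = 1 the ratio reduces to (1 + r)/2, and the standard error falls by about 23%, 13% and 8%. The gain vanishes when the slope of post on pre, rk, equals 1, as at k = 2, r = 0.5.

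Simulation with 18 patients and six sessions gave about 0.62, 0.76 and 0.89 at k = 1, and 0.82 to 1.02 for k from 1.5 to 2. Values just above 1 reflect the small cost of estimating the coefficient.

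**A single arm's change against 0.** With three treatments given equally often, one third of an arm mean's within-patient variance comes from the grand mean, which a centred covariate leaves alone. Two thirds come from the arm's deviation from it. At k = 1 the ratio is 1/3 + (2/3)(1 + r)/2 = (2 + r)/3, or 0.73, 0.83 and 0.90. If patients also differ in true change, with an SD equal to the session SD, simulation gave 0.90, 0.94 and 0.97.

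**Carryover.** Suppose an ECT session shifts the next session's pre- and post-treatment scores equally. Change scores cancel the shift; adjustment cancels only part of it. If each block of three is an independent random ordering, a sham session in position 2 or 3 always follows ECT, while an ECT session there follows sham half the time. Position 1 does not differ by arm. The arms then differ in exposure to the shift by (2/3)(1/2) = 1/3. At k = 1 the bias from a 1-SD shift is roughly (1 − r)/3: 0.27, 0.17 and 0.10 SD. Simulation gave about 0.08 to 0.21 SD, which is lower because the shift itself raises the pre/post slope. A term for the preceding treatment removed the bias but raised the variance by about 12 to 26%.

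**The case against.** The strongest reply is that the size is unknown. Scores taken from the return of responsiveness after anaesthesia need not have the spread of an awake baseline, and at k = 1.5 to 2 most of the gain disappears. That stands, and it is why the range has to be shown over k as well as r.

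Second, both readouts in 2.5.2 use arm-level intervals, for which the gain is smaller than for a contrast. That also stands.

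Third, unadjusted change has a merit of its own: it cancels a carryover shift common to pre- and post-treatment scores. The protocol's background (section 2.1.2) itself describes confusion building up before successive sessions, so this is not idle. One preceding-treatment term would not capture accumulation over several sessions.

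Fourth, silence is not exclusion. The covariates in 2.5.1 are listed for differences in response to stimulation, the response scale is never given, and section 2.5 calls the study exploratory. Baseline could also be fitted as a level of the response, which would weaken the point. Nothing in the documents says so, and the four times in 2.6 all follow treatment. The ambiguity is itself a reason to write the model down.

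**Conclusion.** The point holds in a limited form. On its natural reading the plan uses an unadjusted change score for a primary outcome, and a covariate already collected could sharpen the between-arm contrasts by anything from nothing to about 40% of the variance. The conclusion rests on the inferred response scale, on r between 0.2 and 0.7 and k between 1 and 2, and on a linear model. The last is doubtful for bounded scores such as motor praxis accuracy, which the appendix expects to be near 100%.

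Three stronger readings are not supported:

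- A reader might infer that adjustment would save 15-40% of patients. That takes the k = 1 row alone and applies it to a sample size computed in minutes.
- A reader might infer that subtracting baseline adds noise unless pre and post are very highly correlated. Against the post-treatment score alone, change is noisier only when 1 + k² − 2rk > k², that is r < 1/(2k). At equal SDs the threshold is 0.5, inside the assumed range.
- A reader might infer that all primary outcomes are affected. Time to responsiveness and 3D-CAM delirium are not.

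**What to change.** In 2.5.1 and 2.5.2:

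1. State that the response is change from the same session's pre-treatment score, so that 0 keeps its meaning.
2. Add the session baseline as a deviation from the patient's own mean, with its interaction with time, and the patient's mean baseline as a separate term.
3. Report marginal responses at the average baseline, and keep day of treatment in the model.
4. As sensitivity analyses, report the unadjusted change-score model and a model with a term for the preceding session's treatment. Say that the latter costs precision, which can cancel the gain, and that the adjusted model can carry a small bias if earlier sessions shift both scores.

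The cost is plan wording and a few coefficients per model. No visit, test or procedure changes. In the simulations at unequal SDs, adjustment raised the contrast variance by about 2% at worst, apart from any carryover bias.

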### **Post-treatment:**

Recovery of consciousness (ROC) will be defined as the first time at which subjects correctly responded to two consecutive audio loop commands. At this time, defined as t = 0 minutes, the subject will begin the neurocognitive battery of tests followed by a brief resting period. Neurocognitive testing will be repeated at t= 30, 60, and 90 minutes following emergence while the 3D-CAM will be completed at time 0 and every hour (Table 1) until the patient is scored negative for delirium. Each battery of neurocognitive testing will take

approximately 15-20 minutes to complete. During the rest period, EEG recording will occur with 5 minutes eyes open and 5 minutes eyes closed. At the 90 timepoint patients will not only complete the COGNITION cognitive test but also the 3D-CAM (if positive for delirium at t=60, PROMIS-CAT, Self-Assessment Manikin, and a questionnaire regarding patients' subjectivity of whether they received ECT. Subjects will be permitted to take a brief break to use the restroom and eat or drink, as necessary. Subjects will be discharged according to standard post-anesthesia care unit discharge criteria upon completing the last neurocognitive test battery. A study site coordinator will contact each subject within 24 hours of the study day to document any adverse events.

Assessment	Baseline (Pre-ECT)	Time 0	Time 30	Time 60	Time 90
COGNITION Neurocognitive Testing	х	Х	Х	Х	Х
3D-CAM - Delirium (3D- Confusion Assessment Method)	х	х		х	х
PROMIS-CAT - (Computer Adaptive Testing for depression)	Х				х
Mood Self-Assessment Manikin - mood	Х				х
Scale of Suicidal Ideation	х				
Assessment for Blinding Quality					х

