### Table 1: Assessment at Each Experimental ECT Treatment (Visit 2-Visit 7):

### 2. Description of Assessments:

### Neurocognitive testing (COGNITION battery)

This battery for individualized neurocognitive assessment of fatigue has been tested in the context of sleep deprivation and is administered via a laptop. The effects of ECT and/or an induction dose of an intravenous general anesthetic (ketamine or etomidate) on all the tests below have not previously been well characterized.

During administration, the order will be pseudorandomized, with a full complement given at each testing block. Additionally, the first test for each block will be repeated at the end to address temporal order within the block.

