### Psychomotor Vigilance Test (PVT)

The psychomotor vigilance test (PVT) measures sustained attention by recording reaction time to visual stimuli that are presented at random intervals. During the PVT, subjects are instructed to respond to a small red counter that appears at unpredictable intervals and reports time elapsed in milliseconds by clicking the space bar as soon as the counter appeared. This task is time limited as any response time greater than 500 milliseconds is recorded as a lapse or error of omission. The standard score for the PVT is based on response time and false starts. Originally, the PVT was designed for administration during 10-minute sessions. However, a shorter, modified PVT that remains sensitive to acute total sleep deprivation and chronic partial sleep deprivation was developed. Therefore, the PVT component of each neurocognitive battery in this study will be 3 minutes in duration. An advantage of using this task is that PVT is unaffected by learning and aptitude.

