#### Digit Symbol Substitution Test (DSST)

During the digit symbol substitution test, subjects are presented with a key showing ten symbols and a number (0-10) that correspond with each. Symbols are presented on the center of the screen one at a time, and the subject must type the corresponding number as quickly as possible. This test measures complex scanning, visual tracking, attention, working memory, and visuomotor and visuospatial speed. The standard

score for this task is determined by accuracy and speed, with a severe scoring penalty based on response time. While learning effects can be observed in healthy individuals, individuals who chronically receive only 6 hours of sleep do not improve in this task over time while individuals who chronically sleep less than 6 hours display decline in performance over time. Similarly, acutely sleep deprived individuals display significantly decreased correct responses in this task.

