### Abstract Matching (AM)

Abstract matching (AM) examined abstraction and cognitive flexibility. During the abstract matching task, participants are presented with a single colored geometric shape as well as two sets of geometric shapes.

They then must choose the set that the object completes. Following each selection, the subject is told whether their selection was correct or not are able to use this feedback to determine the implicit rules that govern this task. The standard score for this task is determined by accuracy with a penalty based on mean response time. Cognitive flexibility or "divergent" thinking is significantly impaired by sleep deprivation. The AM task version used in this study was chosen because it can be completed in less than 4 minutes as compared to previous versions, which required 15-20 minutes for completion.

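### Recovery is dated against a change of 0 although the battery is repeated within each session; if DSST or AM scores rise with practice, those tests are dated as recovered too early relative to PVT

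*Combined protocol and SAP*

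**What the plan says.** Section 2.5.2 (Recovery of Cognition) is concerned with "the time needed for the return of cognition to baseline on individual sessions". It fits separate mixed models to reaction time and accuracy and finds when the three treatments' 95% intervals converge. For recovery to baseline it then states: "we will determine the time when the same 95% confidence intervals include 0". Section 2.3.8 says of the reference: "Baseline assessments will be performed at each session immediately prior to ECT". The plan does not say that the response is change from that battery, but on no other natural reading would 0 stand for baseline.

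Appendix 1 (Post-treatment) has a first battery at return of consciousness (t = 0) and adds: "Neurocognitive testing will be repeated at t= 30, 60, and 90 minutes following emergence". Table 1 agrees.

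On learning, Appendix 2 differs by test:

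- DSST: "While learning effects can be observed in healthy individuals", followed by the remark that people on chronically short sleep do not improve.
- PVT: "An advantage of using this task is that PVT is unaffected by learning and aptitude".
- AM: after each choice patients are told whether it was right and are "able to use this feedback to determine the implicit rules that govern this task". Carry-over to a later administration is not stated.
- MPT, F2B and VOLT: nothing on practice.

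Section 2.5.1 models time and treatment as fixed effects and considers day of treatment. It has no term for repetition within a session.

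**The concern.** A change of 0 shows that the patient has regained the pre-session score. It shows that function is restored only if repeating the test leaves an unimpaired person's score unchanged. The protocol claims this for PVT and suggests the opposite for DSST. On a test with a practice gain, an unimpaired patient would score on the favourable side of 0, and a mean change of 0 would hide a deficit equal to the gain.

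This matters because the first study objective is the order in which cognitive functions recover, and aim 4 compares that order with recovery from isoflurane. If 0 is the unimpaired value for one test and not for another, part of the observed order may reflect how learnable the tests are. Healthy volunteers may also learn at a different rate from these patients, which would affect the comparison of recovery times with the isoflurane cohort.

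**Working it through.** **Is practice separable from recovery?** Batteries per session: 1 before + 4 after = 5. In every arm, t = 0, 30, 60 and 90 are administrations 2, 3, 4 and 5, so time and repetition are fully aliased within a session. (Section 2.3.8 describes testing up to two hours, which would add a sixth battery; it should be reconciled with Table 1, but the aliasing is the same.) Candidate safeguards:

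- A fresh baseline each session and the day-of-treatment term deal with learning between sessions, not within one.
- Appendix 2 says "the first test for each block will be repeated at the end to address temporal order within the block", which concerns order inside a battery.
- No session is without anesthesia, and the isoflurane volunteers are also recovering from an anesthetic, so no group shows the gain alone.

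**How far could the date move?** The plan gives no figure for practice, so there is none to reproduce. Its only scale is the expected difference of 20-40 minutes in section 2.6. The illustration below takes n = 15-20 from the plan and assumes the rest:

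- change-score SD 1 per session; two sessions per treatment, correlated 0.3
- initial deficit 2 SD, halving every 20 minutes
- constant practice gain g of 0, 0.2, 0.3 or 0.5 SD at all post-treatment batteries

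Standard error of the arm mean = sqrt(((1 + 0.3)/2)/n) = sqrt(0.65/n).

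- n = 15: 0.208; t quantile 2.145; half-width w = 0.446 SD
- n = 20: 0.180; t quantile 2.093; half-width w = 0.377 SD

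Mean change at time t is g − 2 × 2^(−t/20). The interval first includes 0 when the remaining deficit equals w + g, so the rule fires at t = 20 × log2(2/(w + g)).

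| Gain g (SD) | n = 15: fires at (min) | Earlier by | n = 20: fires at (min) | Earlier by | True deficit left (SD) |
|---|---|---|---|---|---|
| 0 | 43.3 | – | 48.1 | – | 0.45 / 0.38 |
| 0.2 | 32.6 | 10.7 | 35.9 | 12.3 | 0.65 / 0.58 |
| 0.3 | 28.4 | 14.8 | 31.2 | 16.9 | 0.75 / 0.68 |
| 0.5 | 21.6 | 21.7 | 23.8 | 24.3 | 0.95 / 0.88 |

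**A second model.** Let the gain accumulate as g × (1 + t/30), with sessions correlated 0.5, initial deficit 1-2 SD and half-life 20-40 minutes. The date then moves earlier by:

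| Gain per repetition (SD) | n = 15 (min) | n = 20 (min) |
|---|---|---|
| 0.05 | 4-17 | 5-20 |
| 0.10 | 8-27 | 9-32 |
| 0.20 | 12-40 | 15-47 |

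In both models the shift is zero if the gain is zero.

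**What is unaffected.** At a fixed time all arms are at the same repetition. A gain common to the arms cancels from the difference between them.

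**The case against.** The strongest reply is that no bias has been shown. The DSST remark is about healthy people and is paired with a statement that sleep-restricted people do not improve. Section 2.1.2 describes disturbed attention and memory after ECT. Patients have also met the battery at Visit 1 and before every session, so they may have reached a plateau, and fatigue could offset any gain. This stands: the effect is conditional, and its direction is not certain.

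A second reply is that the stated target is return to baseline, for which 0 is the right reference. This also stands. The difficulty begins when the date is read as restored function or compared across tests. A third reply is that the plan already compares arms at the same time through convergence of the intervals. That is correct, and it protects the treatment comparison.

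Three stronger readings are tempting but not supported:

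- **That every test except PVT is affected.** Learning is stated for DSST only and at most suggested for AM.
- **That a patient group ending better than baseline would be classed as never recovered.** A modelled trajectory rising continuously from a deficit meets 0 on the way, so it is dated as recovered before its interval can lie wholly above 0. The case arises only if the rule is read at the discrete test times and the estimate jumps over 0, or if there was no deficit at the start.
- **That the rule's date is where the mean change reaches 0.** Under the first model that is 66, 55 or 40 minutes for gains of 0.2, 0.3 or 0.5 SD. The rule fires earlier, when the interval first includes 0.

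The table also shows that the rule fires with 0.38-0.45 SD of deficit left even without practice. That is the separate matter of treating non-significance as recovery.

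**Conclusion.** The point holds in a limited, conditional form. The recovery rule uses one reference, 0, for tests that the protocol itself describes as differing in learning, and the design and model cannot separate practice from recovery within a session. If there is a net within-session gain, the DSST date, and possibly the AM date, is too early relative to PVT. The order of domains and the comparison with the isoflurane volunteers carry that error.

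Under the first set of assumptions the shift is about 11-12, 15-17 or 22-24 minutes at gains of 0.2, 0.3 or 0.5 SD. The two larger shifts are around the lower end of the 20-40 minute effects in section 2.6; the smallest is below it. Every input except n is assumed. The study is declared exploratory and the treatment contrast is sound, so this is an inexpensive improvement to the primary analysis text, not a fault that undermines the trial.

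**What to change.** In section 2.5.2:

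1. State that the response is change from the same session's pre-treatment score. Report the absolute DSST and AM times as return to the pre-session score, not as restored function. Base conclusions about treatment on the same-time between-arm comparison already planned.
2. Add a sensitivity analysis that replaces 0 by a plausible practice gain over a stated range, and show whether the order of domains changes. The repeated first test in the pre-treatment battery can inform the range: 15-20 patients × 6 sessions = 90-120 pairs, with no anesthetic between the two administrations. Its limits should be stated. It covers one repetition and mixes practice with fatigue. The initial task is also part of the 18 randomized combinations in section 2.3.6, so if that task is fixed per patient the pairs for a given test may come from few patients, or some tests may have none.
3. Make explicit that recovery is dated at the first time the interval is no longer wholly on the impaired side of the reference, which removes doubt about intervals beyond it.

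The cost is SAP wording and one rerun of existing models, with no new data. The downside is that some DSST and AM recovery times, and the domain order, will carry a caveat or be given as a range.
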